1. INTRODUCTION

Philadelphia chromosome-positive (Ph+) acute lymphoblastic leukemia (ALL): Ph+ ALL is an aggressive subtype of ALL characterized by the presence of the *BCR-ABL1* gene fusion.¹ Historically, the outcomes of patients with Ph+ ALL were dismal, with a 3-year disease-free survival rate of <15%.² However, with the incorporation of tyrosine kinase inhibitors (TKIs) into chemotherapy-based treatment regimens, survival rates of 30-80% have been achieved, with improved long-term survival seen in patients receiving later-generation TKIs.³-5 These TKIs target the aberrant Bcr-Abl1 protein, which is the primary driver of proliferation and survival of the Ph+ leukemic cells. With the combination of chemotherapy and a TKI, complete remission (CR) rates >90% can be achieved.⁴-7 Despite this high CR rate seen with TKI and chemotherapy combination regimens, many patients subsequently relapse; for these patients, outcomes are dismal and there is no clear standard of care. Recent evidence suggests that the bispecific T-cell engaging antibody, blinatumomab, has significant antilleukemic efficacy for these patients.⁸ However, even with this promising treatment, the overall response rate is only 36% and the median OS is approximately 7 months. Therefore, novel treatment options are needed for patients with Ph+ ALL who are refractory or relapse after initial treatment.

Ponatinib: Ponatinib is a later-generation TKI that is capable of inhibiting the T315I BCR-ABL1 kinase mutation, which commonly arises during treatment with other TKIs such as imatinib or dasatinib. In the phase II PACE trial of single-agent ponatinib in patients with relapsed/refractory Ph+ leukemias, ponatinib resulted in major hematologic response in 41% of patients with Ph+ ALL. However, the vast majority of patients relapsed, and the 1-year progression-free survival was only 7%. These results demonstrate that ponatinib has activity in relapsed and TKI-resistant Ph+ ALL, although as a single agent it does not appear to produce durable responses. In contrast, when combined with hyper-CVAD chemotherapy in patients with newly diagnosed Ph+ ALL, the ponatinib-containing regimen resulted in a CR rate of 100% with 2-year event-free

survival (EFS) and overall survival (OS) rates of 81% and 80%, respectively. Ponatinib can be associated with cardiovascular toxicity, including arterial and thromboembolic events; however, using risk-adapted dosing schedule of ponatinib may reduce this risk. Historical comparisons suggest the results achieved with the combination of hyper-CVAD plus ponatinib may be superior to those achieved with hyper-CVAD plus dasatinib.

Venetoclax: Venetoclax (formerly ABT-199/GDC-0199) is a potent, selective and orally bioavailable small molecule BCL-2 inhibitor that has shown promising anti-leukemia activity in patients with relapsed or refractory chronic lymphocytic leukemia (CLL) as monotherapy and modest single agent activity in select subtypes of acute myeloid leukemia ¹²⁻¹⁴; venetoclax is currently FDA approved for the treatment of patients with CLL with del(17)(p13.1) by interphase cytogenetics who have received at least one prior therapy. For patients with AML, combination therapy with venetoclax and other agents appears to be more efficacious that venetoclax monotherapy. ¹⁵ BCL-2 is an anti-apoptotic protein that is over-expressed in many hematologic malignancies and is associated with tumor initiation, disease progression and drug resistance. ¹⁶ BCL-2 mRNA is highly expressed in multiple subtypes of ALL compared with normal pre-B controls. ¹⁷ Recent reports demonstrated that primary B-lineage ALL cells each express high levels of BCL-2 and exhibit significant sensitivity to BCL-2 inhibition by venetoclax, resulting in rapid apoptotic cell death. ¹⁸ Specifically, Ph+ ALL appears to be dependent on BCL-2 for survival; consequently, BCL-2 inhibition has been shown to result in apoptosis of Ph+ ALL cell lines. ¹⁹

Rationale for Combination of Ponatinib and Venetoclax: The combination of venetoclax and targeted BCR-ABL1 TKIs has been explored in preclinical studies of Ph+ ALL.20 In one study, the combination of venetoclax with various TKIs resulted in synergistic in vitro inhibition of cell growth and induction of apoptosis. While this synergy was seen across a number of TKIs tested, this effect was most pronounced when venetoclax was combined with either dasatinib or ponatinib. The synergistic inhibition of leukemic growth was likely mediated by the ability of these two TKIs to target the Lck/Yes novel (LYN) tyrosine kinase in addition to ABL. Combination of venetoclax with an inhibitor of LYN resulted in increased expression of the pro-apoptotic BCL-2-like protein 11 (BIM) and lower expression of the anti-apoptotic myeloid cell leukemia 1 (MCL-1). In a patientderived xenograft ALL mouse model, the combination of a LYN-targeting TKI and ponatinib appeared to prevent the increase in MCL-1 with venetoclax treatment, which is an established mechanism of venetoclax resistance. These findings provide a strong rational for the combination of venetoclax with ponatinib, a potent anti-BCR-ABL1 kinase inhibitor that also targets the LYN tyrosine kinase. This combination approach can also test the hypothesis that inhibition of LYN by ponatinib can alter the balance of apoptotic proteins in favor of a profile that increases leukemia cells' sensitivity to BCL-2-targeted therapies.

Summary: There is an unmet need for novel treatment strategies for patients with relapsed or refractory Ph+ ALL. Ponatinib is a potent anti-BCR-ABL1 TKI capable of inducing deep and long-term remissions when combined with chemotherapy in patients with newly diagnosed Ph+ ALL. Venetoclax also shows promise in the treatment of a number of leukemias and other hematologic malignancies that are dependent on the anti-apoptotic protein BCL-2 for survival. Furthermore, preclinical data suggest that the combination of ponatinib and venetoclax may have synergistic effect in Ph+ ALL, mediated through the targeting of the LYN tyrosine kinase. Taken together, these preclinical and clinical studies provide a strong rationale for a phase I/II trial combining venetoclax with ponatinib in patients with relapsed/refractory Ph+ ALL.

2. STUDY OBJECTIVES AND ENDPOINTS

2.1. Primary Objectives

- Phase I: To determine the maximum tolerated dose (MTD) of venetoclax, ponatinib and dexamethasone in patients with relapsed/refractory Ph+ ALL or lymphoid BP-CML
- Phase II: To determine the efficacy of the regimen, as defined by the rate of complete remission (CR) or CR with incomplete count recovery (CRi)

2.2 Secondary Objectives

- To determine efficacy outcomes, including rate of minimal residual disease negativity by PCR for BCR-ABL1 transcripts, median relapse-free survival, and median overall survival
- To determine the proportion of patients proceeding to allogeneic stem cell transplant (ASCT)
- To preliminarily determine the safety of the combination regimen

2.3 Exploratory Objectives

- To evaluate the effect of single-agent ponatinib on apoptotic proteins and Bcl-2 dependency
- To correlate apoptotic protein expression and Bcl-2 dependency on response and resistance to the combination regimen
- To assess impact of baseline genomics on outcomes with the combination regimen

3. SELECTION OF PATIENTS

Patients will be selected from those referred to the Leukemia department at M D Anderson Cancer Center through the normal of process of referral. Eligible patients will be registered after the process of consenting on the MD Anderson protocol and data monitoring system.

3.1 Inclusion Criteria

- Patients ≥ 18 years of age with relapsed/refractory Ph+ ALL or lymphoid blast phase CML [either t(9;22) and/or BCR-ABL1 positive by fluorescent in situ hybridization or polymerase chain reaction], including prior therapy with at least one Bcr-Abl tyrosine kinase inhibitor
- 2. Performance status ≤3 (ECOG Scale)
- 3. Adequate liver and renal function as defined by the following criteria:
 - a) Total serum bilirubin ≤ 1.5 x upper limit of normal (ULN), unless due to Gilbert's syndrome, hemolysis or the underlying leukemia approved by the PI
 - Alanine aminotransferase (ALT) ≤ 1.5 x ULN, unless due to the underlying leukemia approved by the PI
 - c) Aspartate aminotransferase (AST) ≤ 1.5 x ULN unless due to the underlying leukemia approved by the PI
 - d) Creatinine clearance ≥30 mL/min
- 4. Adequate pancreatic function as defined by the following criteria:
 - a) Serum lipase and amylase ≤ 1.5 x ULN
- 5. Ability to swallow
- 6. Signed informed consent

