3.2 Exclusion Criteria

- 1. Prior history of treatment with venetoclax. Prior ponatinib is allowed.
- 2. Active serious infection not controlled by oral or intravenous antibiotics (e.g. persistent fever or lack of improvement despite antimicrobial treatment).
- 3. History of acute pancreatitis within 1 year of study or history of chronic pancreatitis
- 4. Uncontrolled hypertriglyceridemia (triglycerides > 450mg/dL)
- Active secondary malignancy that in the investigator's opinion will shorten survival to less than 1 year.
- Active Grade III-V cardiac failure as defined by the New York Heart Association Criteria
- Clinically significant, uncontrolled, or active cardiovascular disease, specifically including, but not restricted to:
 - History of myocardial infarction (MI), stroke, revascularization, unstable angina or transient ischemic attack within the past 12 months
 - Left ventricular ejection fraction (LVEF) less than lower limit of normal per local institutional standards prior to enrollment
 - Diagnosed or suspected congenital long QT syndrome
 - Any history of clinically significant atrial or ventricular arrhythmias (such as uncontrolled artrial fibrillation, ventricular tachycardia, ventricular fibrillation, or Torsades de pointes) as determined by the treating physician
 - Prolonged QTc interval on pre-entry electrocardiogram (> 480 msec) unless corrected after electrolyte replacement
 - History of venous thromboembolism including deep venous thrombosis or pulmonary embolism within the past 3 months. Patients with a history of catheter associated upper extremity venous thromboembolism are not excluded.
 - Uncontrolled hypertension (diastolic blood pressure >100mmHg; systolic >150mmHg).
- 8. Patients currently taking drugs that are generally accepted to have a high risk of causing Torsades de Pointes (unless these can be changed to acceptable alternatives)
- 9. Received strong or moderate CYP3A inhibitors or inducers within 3 days of study entry
- 10. Consumed grapefruit, grapefruit products, Seville oranges, or star fruit within 3 days prior to starting venetoclax
- 11. Treatment with any investigational antileukemic agents or chemotherapy agents in the last 7 days before study entry, unless full recovery from side effects has occurred or patient has rapidly progressive disease judged to be life-threatening by the investigator. Prior recent treatment with corticosteroids and hydroxyurea is permitted.

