6. STUDY PROCEDURES

6.1. Pre-Treatment Evaluation

- 1. History and physical examination, including height and weight, vital signs (blood pressure, respiratory rate, pulse and temperature) and ECOG performance status 2. Concomitant medication and medical history assessment within 24 hours of first dose
- 3. CBC with differential, electrolytes (potassium, calcium, magnesium, phosphorus), LDH, uric acid, creatinine, liver function tests (AST, ALT, total bilirubin), lipase, amylase, triglycerides, hepatitis B antibodies
- 4. Bone marrow aspirate, cytogenetics and PCR for BCR-ABL1. Quick Philadelphia screen (FISH) is acceptable.
- 5 ÈKG
- 6. Pregnancy test in female patients of appropriate age and menopausal state within 1 week of first dose
- 7. Echocardiogram or MUGA scan to assess cardiac function
- 8. Biomarker studies including CyTOF, BH3 profiling, and next-generation targeted sequencing and SNP array (performed on bone marrow and peripheral blood)

All pretreatment evaluation must be performed within 2 weeks of first dose of the study drug, unless otherwise specified as above.

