7. EFFICACY AND SAFETY ASSESSMENTS

7.1. CRITERIA FOR RESPONSE

- Complete Remission (CR): Normalization of the peripheral blood and bone marrow with 5% or less blasts in normocellular or hypercellular marrow with a granulocyte count of 1 x 10⁹/L or above, and platelet count of 100 x 10⁹/L. Complete resolution of all sites of extramedullary disease is required for CR.
- Complete remission without recovery of counts (CRi): Peripheral blood and marrow results as for CR, but with incomplete recover of counts (platelets < 100 x 10⁹/L; neutrophils < 1 x 10⁹/L).
- 3. Complete cytogenetic response (CCyR): Same as for CR with cytogenetics showing diploid karyotype (valid only for patients with abnormal cytogenetics at enrollment)

²After achieving CR/CRi, bone marrow should be performed every 2-3 cycles or as clinically indicated.

³In patients without recent ponatinib exposure, BH3 profiling will be assessed on days 1 and 7 of cycle 1, CyTOF will be assessed on days 1, 7 and 35 of cycle 1. In patients with recent ponatinib exposure, BH3 profiling will be assessed on day 1 of cycle 1, CyTOF will be assessed on days 1 and 28 of cycle

^{1.} CyTOF and BH3 profiling will also be performed at the time of relapse.

4Amylase and lipase will be checked in all patients at screening. Subsequent amylase and lipase only

need to be checked as clinically indicated (e.g. for patients with abdominal pain)

⁵ Concomitant medication data will not be entered into the case report form (Prometheus); however, concomitant medications will be documented in the subject's electronic medical record.

⁶ Biomarker studies will not be captured in the case report form.

- Complete molecular response (CMR): Same as for CR with RT-PCR for BCR-ABL <0.01% ²¹
- Major molecular response (MMR): Same as for CR with RT-PCR for BCR-ABL with 3 log reduction from baseline (for p190 transcripts) and/or ≤0.1% by the International Scale (for p210 transcripts)
- Partial Response (PR): As above for CR except for the presence of 6-25% marrow blasts
- 7. Progressive Disease (PD): increase of at least 25% in the absolute number of circulating or bone marrow blasts or development of extramedullary disease
- Relapse Disease: reappearance of blasts in the blood or bone marrow >5% or development of extramedullary disease after initial response.

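### Relapsed/refractory status is not tied to the pretreatment marrow, so a patient already at 5% or fewer blasts can count as a CR/CRi responder in the primary OR

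*Combined protocol and SAP*

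**What the plan says.** **Entry.** Section 3.1, item 1, requires "relapsed/refractory Ph+ ALL or lymphoid blast phase CML [either t(9;22) and/or BCR-ABL1 positive by fluorescent in situ hybridization or polymerase chain reaction", with at least one earlier BCR-ABL inhibitor. No item in 3.1 or 3.2 gives a minimum blast percentage or asks for extramedullary disease, and neither refractory nor blast phase is defined. Section 3.2, item 11, states: "Prior recent treatment with corticosteroids and hydroxyurea is permitted". Section 4.2 makes specific provision for patients who took ponatinib in the two weeks before starting.

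**Baseline.** Section 6.1, item 4, calls for "Bone marrow aspirate, cytogenetics and PCR for BCR-ABL1. Quick Philadelphia screen (FISH) is acceptable". The general window is two weeks before first dose. No result is required for entry or for the analysis.

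**Response.** Section 7.1 defines CR as "Normalization of the peripheral blood and bone marrow with 5% or less blasts in normocellular or hypercellular marrow", with count recovery and no remaining extramedullary disease. CRi is "Peripheral blood and marrow results as for CR, but with incomplete recover of counts". Complete cytogenetic response alone carries a baseline condition: it is "valid only for patients with abnormal cytogenetics at enrollment". Relapse is "reappearance of blasts in the blood or bone marrow >5% or development of extramedullary disease after initial response".

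**Analysis.** Section 10 takes CR or CRi after two cycles as the primary OR and scores dropouts before that point as failures. It places phase I patients treated at the MTD in every efficacy analysis and calls the regimen worth pursuing at an OR of at least 60%. It has no rule for a patient who starts at or below 5% blasts.

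**The concern.** A state-based endpoint measures drug effect only in patients who are not already in that state. Here the primary endpoint is met by having 5% or fewer marrow blasts and no extramedullary disease; CRi removes the count requirement. Nothing in the eligibility criteria, the work-up or the analysis plan ensures that a patient starts above that line.

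The most credible route is a patient with genuine relapsed or refractory disease whose blasts fell to 5% or below before the pretreatment marrow, on steroids, hydroxyurea or ponatinib. If nothing then changes over two cycles, that patient adds one response to the primary OR and one to the Table 3 count.

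The trial has one arm and judges the result against a fixed 60%, so no control group would show the shift. The error is upward as long as these patients score CR/CRi more often than the others, which is to be expected. It both eases the 60% criterion and weakens the futility rule.

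**Working it through.** **Inputs from section 10:** maximum 26 patients; success at an OR of at least 60%; Beta(1.2, 0.8) prior for OR; looks at 6 patients and then every 2. Since 0.60 × 26 = 15.6, success means 16 or more responders. **Assumed, because the documents do not give it:** the number m (or share f) of patients already at 5% blasts or fewer without extramedullary disease.

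**Step 1. Reproduce the plan.** With posterior Beta(1.2 + x, 0.8 + n − x) and stopping when P(OR < 0.60 | data) > 0.975, every Table 3 boundary is recovered (0 of 6, up to 1 of 8, and so on to 9 of 24). At OR 60% and toxicity 15%, the early-stopping probability is 1 − (1 − 0.0504)(1 − 0.3601) = 0.3924, as stated. All 25 tabulated probabilities reproduce. The equal-tail interval for 16/26 is (0.431, 0.782) against the stated (0.43, 0.79), a difference that does not matter here. The gap is one of definition, not arithmetic.

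**Step 2. Worst-case effect on the success criterion.** Let p be the true OR in patients with active disease at baseline, let all m others score CR/CRi, and ignore early stopping.

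Expected OR = ((26 − m)p + m)/26. 
P(at least 16/26) = P(Bin(26 − m, p) ≥ 16 − m).

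| m | Expected OR, p = 50% | P(≥16/26) | Expected OR, p = 40% | P(≥16/26) |
|---|---|---|---|---|
| 0 | 50.0% | 0.1635 | 40.0% | 0.0217 |
| 2 | 14/26 = 53.8% | 0.2706 | 11.6/26 = 44.6% | 0.0535 |
| 3 | 14.5/26 = 55.8% | 0.3388 | 12.2/26 = 46.9% | 0.0813 |
| 5 | 15.5/26 = 59.6% | 0.5000 | 13.4/26 = 51.5% | 0.1744 |

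**Step 3. At the margin.** Suppose 16/26 (61.5%) is observed and k of the responders began at 5% or fewer. Setting them aside gives (16 − k)/(26 − k): 15/25 = 60.0% for k = 1, and 14/24 = 58.3% for k = 2. Two such patients are enough to cross the criterion.

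**Step 4. Relax both simplifications.** Apply the Table 3 looks and let each such patient score CR/CRi with probability s. The scored rate is q = f·s + (1 − f)p. With p = 40%:

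| f | s | q | Futility stop | Not stopped for futility and ≥16/26 |
|---|---|---|---|---|
| 0 | – | 0.40 | 57.5% | 2.2% |
| 10% | 1 | 0.46 | 35.4% | 8.2% |
| 20% | 1 | 0.52 | 17.8% | 21.9% |
| 10% | 0.8 | 0.44 | 42.5% | 5.5% |
| 20% | 0.8 | 0.48 | 28.8% | 11.8% |

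Allowing for the futility looks barely changes the success probabilities. Letting s fall below 1 reduces them a good deal: at f = 20% the chance drops from 21.9% to 11.8%, still above 2.2%.

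**The case against.** The strongest reply is that the protocol's vocabulary already presumes active disease. Section 7.1 puts relapse above 5% blasts, section 7.3 treats non-response as failure to reach CR/CRi, cycle 1 is called induction, and CR is worded as normalization. A PCR-positive patient at 3% blasts falls in the section 4.3 category of CR/CRi without CMR, which is a remission category. That argues against enrolling such a patient simply for molecular persistence, and it stands. But those definitions govern events on study. They are not linked to eligibility or to the screening marrow, and they do not cover a relapsed patient whose blasts were reduced shortly before that marrow. The cytogenetic response definition shows how the authors write a baseline condition when they want one.

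Three stronger readings are tempting, and the documents do not support them:

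- *A positive PCR alone qualifies a patient.* The bracket in inclusion 1 only says how Ph or BCR-ABL1 positivity is shown; relapsed or refractory disease is a separate requirement. The FISH remark in 6.1 likewise concerns Ph testing.
- *The seven-day chemotherapy waivers are a main route in.* One waiver is for rapidly progressive disease, and Table 1 in section 5 excludes anticancer therapy for five half-lives before first dose. Recent ponatinib differs because section 4.2 expressly plans for it.
- *Such responses involve no drug effect at all.* The patient must remain in that state through two cycles, and dropouts are failures. Some of that persistence may be due to the regimen; the endpoint cannot show how much.

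It is also fair that the frequency is unknown and may be zero.

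**Conclusion.** The gap stands as a matter of what the text permits. Entry status is not tied to the pretreatment marrow, CR/CRi has no baseline condition, and section 10 has no rule that would catch the case. The documents do not show that such patients were or will be enrolled, so a reader should not infer a known bias.

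The size is a sensitivity range. If 2 to 5 of 26 patients are affected and all score CR/CRi, with early stopping ignored, the chance of meeting the 60% criterion rises from 0.16 to 0.27-0.50 at a true OR of 50%, and from 0.02 to 0.05-0.17 at 40%. The figures shrink if some of these patients progress or drop out, and vanish if none enrol. The plan's stated boundaries and stopping probabilities are not in question. With a single arm, a fixed benchmark and a margin that two patients can cross, the gap should be closed.

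**What to change.** **Preferred: inclusion 1.** Require that the pretreatment assessment already mandated in 6.1 shows more than 5% blasts in marrow or blood, or extramedullary disease. This is the protocol's own threshold from 7.1. Tables 2 and 3 and the operating characteristics stay as they are. The cost is slightly slower accrual.

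**Alternative: section 10.** Define the response-evaluable set for the primary OR and for Table 3 by the same threshold. Amend the sentence that puts MTD-treated phase I patients in all efficacy analyses so that it agrees. Keep the remaining patients in the safety, CMR and OS analyses and list them separately. The costs are a slightly smaller OR denominator and, because Tables 2 and 3 share one patient count, stated joint stopping probabilities that become approximate once any patient is set aside.

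Neither route needs new data or alters treatment. One limit remains under both: the pretreatment marrow may be up to two weeks old, so blast reduction between that sample and day 1 would go unseen.

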3.2 Exclusion Criteria

- 1. Prior history of treatment with venetoclax. Prior ponatinib is allowed.
- 2. Active serious infection not controlled by oral or intravenous antibiotics (e.g. persistent fever or lack of improvement despite antimicrobial treatment).
- 3. History of acute pancreatitis within 1 year of study or history of chronic pancreatitis
- 4. Uncontrolled hypertriglyceridemia (triglycerides > 450mg/dL)
- Active secondary malignancy that in the investigator's opinion will shorten survival to less than 1 year.
- Active Grade III-V cardiac failure as defined by the New York Heart Association Criteria
- Clinically significant, uncontrolled, or active cardiovascular disease, specifically including, but not restricted to:
 - History of myocardial infarction (MI), stroke, revascularization, unstable angina or transient ischemic attack within the past 12 months
 - Left ventricular ejection fraction (LVEF) less than lower limit of normal per local institutional standards prior to enrollment
 - Diagnosed or suspected congenital long QT syndrome
 - Any history of clinically significant atrial or ventricular arrhythmias (such as uncontrolled artrial fibrillation, ventricular tachycardia, ventricular fibrillation, or Torsades de pointes) as determined by the treating physician
 - Prolonged QTc interval on pre-entry electrocardiogram (> 480 msec) unless corrected after electrolyte replacement
 - History of venous thromboembolism including deep venous thrombosis or pulmonary embolism within the past 3 months. Patients with a history of catheter associated upper extremity venous thromboembolism are not excluded.
 - Uncontrolled hypertension (diastolic blood pressure >100mmHg; systolic >150mmHg).
- 8. Patients currently taking drugs that are generally accepted to have a high risk of causing Torsades de Pointes (unless these can be changed to acceptable alternatives)
- 9. Received strong or moderate CYP3A inhibitors or inducers within 3 days of study entry
- 10. Consumed grapefruit, grapefruit products, Seville oranges, or star fruit within 3 days prior to starting venetoclax
- 11. Treatment with any investigational antileukemic agents or chemotherapy agents in the last 7 days before study entry, unless full recovery from side effects has occurred or patient has rapidly progressive disease judged to be life-threatening by the investigator. Prior recent treatment with corticosteroids and hydroxyurea is permitted.
- 12. Pregnant and lactating women will not be eligible; women of childbearing potential should have a negative pregnancy test prior to entering on the study and be willing to practice methods of contraception throughout the study period. Women do not have childbearing potential if they have had a hysterectomy or are postmenopausal without menses for 12 months. In addition, men enrolled on this study should understand the

risks to any sexual partner of childbearing potential and should practice an effective method of birth control. Appropriate birth control will be determined by the treating physician.

